# 11.2 Other Criteria Requiring Discontinuation

Withdrawal of Subjects for reasons other than Non-compliance or Adverse Events:

- Protocol non-adherence: incorrect dosing strategy or other non-adherence points at the judgement of the PI
- Incomplete side effect diary data, defined as missing 20% or more responses

Withdrawn participants will be replaced at a proportion of 1:1. Procedures are as follows:

• Study personnel, investigators, DSMB will be informed of the need for replacement due to participant withdrawal.

Subsequent data to be collected from the withdrawn participant will be restricted to the
minimum amount necessary to continue to monitor safety, i.e., side effect diary including
questions of sedation, LSD short form, dizziness, lightheadedness, bad dreams, nausea,
vomiting, pruritus, hallucinations.

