# 1 Protocol Overview

Study Description	The purpose of this study is to identify a tolerable dose for postpartum ketamine infusion using a maximum tolerated dose (MTD) 3+3 design. A loading dose over 1 hour will be the MTD variable to be tested, as our data suggest that ketamine side effects occur with the loading dose.
Study Population:	Patients having cesarean delivery (CD) who are either: 1) planning not to breastfeed; or 2) are receiving ketamine as part of clinical care, will be enrolled. Ketamine will be started in postpartum patients, after cord clamping.
Planned Sample Size:	The projected sample size will be a maximum of 12 patients with complete primary outcome data within the MTD 3+3 design.
Participating Institutions (if a multicenter clinical trial)	N/A

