# 3.4 Endpoints

# 3.4.1 Primary Endpoint

Maximum Tolerated Dose (MTD). The MTD will be defined as the dose at which fewer than 33% of patients experience a DLT defined by intolerability.

Tolerability (dichotomous Yes/No)

Tolerability (YES) will be defined as: lack of adverse events (adverse event defined as: severe unresolved hemodynamic effect: systolic blood pressure <80 or >160, heart rate <40 or >120).

Lack of Tolerability will be defined as presence of any adverse event (i.e., severe unresolved hemodynamic effect: systolic blood pressure <80 or >160, heart rate <40 or >120).

A **DLT** event is defined by complete infusion cessation due to intolerable side effect acceptability ratings by patient, OR the experience of an intolerable event as defined above. The escalation of dosing will be as noted in Figure 2 and is based on a modified Fibonacci sequence  $^{101,102}$  with smaller proportional increases in dose in the escalation scheme. Escalations occur until 2 in a cohort of 3 to 6 experiences DLT (i.e., until  $\geq$ 33% of patients experience DLT at that dose). The dose **below** this level estimates the MTD.

Participants will be classified as having had a DLT if any of the following conditions are met:

- Persisting (i.e., unresolved after 3 consecutive measurements within a 15-minute interval)
  hemodynamic side effects defined as below and despite treatments or minimizing
  infusion rates as specified.
  - Systolic blood pressure <80 or >160
  - Heart rate <40 or >120
- Complete infusion cessation due to intolerable side effect acceptability ratings by patient

Primary Outcomes will be measured at a minimum of every 4-hours from the start of the ketamine infusion (t = 0) for 24-hours (12-hours post infusion cessation). Additional assessments will be administered between the 4-hour measurements if any adverse event or side effect is noted by the patient.

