# Side Effect Acceptability Ratings

Any reported side effects are rated by patients. Patient reported side effects (i.e., dizziness, lightheadedness, bad dreams, nausea, vomiting, itchiness, and hallucinations: all dichotomous outcomes) will be evaluated based on patient-specific reports of how "acceptable" or "unacceptable" the side effects are for continued or future use of the study medication. Patient-reported acceptability is defined based on theoretical framework of acceptability and focused on constructs of Burden ("Would experiencing side effects keep you from participating in this intervention (ketamine) again?" yes/no) and Affective Attitude ("Based on your experience with this medication, would you be willing to participate in this intervention (ketamine) again?" yes/no).

- 1. Acceptability is the absence of patient-centered unacceptable side effects. Patients with side effects who report that the side effects were "acceptable" on digital diary will be counted as having confirmed **side effect** acceptability ratings, regardless of the presence of any side effects to the ketamine dose. Patient-reported acceptability is defined as a "yes" to Affective Attitude with a "no" to Burden.
- 2. Unacceptability is any patient report of unacceptable side effects, defined as any positive response on the digital side effect diary rated unacceptable by the patient. Either a negative response to Attitude, or a positive response to Burden, will define patient unacceptability.

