#### Side Effect Acceptability Ratings.

Our existing and previously tested **digital diary** will automate alerts for questions about side effects after infusion start at 15-, 30-, 60- minutes, and every 4 hours in the first 24 hours after infusion start (Figure 1, section 1.1). The diary has been tested and used by our group in previous work; alerts coincide with RASS assessments and similar timing of clinical assessments for routine CD nursing care and monitoring (i.e., is not more burdensome or intrusive to patients than routine clinical post-CD care). The digital diary will assess side effects

(i.e., dizziness, lightheadedness, bad dreams, nausea, vomiting, itchiness, and hallucinations: all dichotomous outcomes). Any positive response to any item will trigger the subject to rate their acceptability of side effects in the following way. Patient-reported acceptability is defined based on theoretical framework of acceptability and focused on constructs of *Burden* ("Would experiencing side effects keep you from participating in this intervention (ketamine) again?" yes/no) and *Affective Attitude* ("Based on your experience with this medication, would you be willing to participate in this intervention (ketamine) again?" yes/no). Either a negative response to Attitude, or a positive response to Burden, will define patient unacceptability.

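### Section 11.2 replaces dosed patients for as few as two missed diary entries without tying the rule to DLT evaluability, so some patients with a known DLT status are replaced

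*Combined protocol and SAP*

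**What the plan says.** Section 11.2 lists two criteria for withdrawal other than adverse events. The second is "Incomplete side effect diary data, defined as missing 20% or more responses". The judgement of the PI is attached to the first criterion (protocol non-adherence), not to this one. The consequence follows directly: "Withdrawn participants will be replaced at a proportion of 1:1". Data collected after withdrawal are limited to the "minimum amount necessary to continue to monitor safety, i.e., side effect diary including" a list of symptoms; vital signs are not on that list.

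Section 1 defines the sample differently: "The projected sample size will be a maximum of 12 patients with complete primary outcome data within the MTD 3+3 design".

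Section 3.4.1 gives two ways to have a DLT. One is a persisting blood pressure or heart rate abnormality. The other is "complete infusion cessation due to intolerable side effect acceptability ratings by patient". Primary outcomes are followed for 24 hours from infusion start. Section 4 refers the reader to 3.4.1 for the DLT definition.

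Under Side Effect Acceptability Ratings in Section 3.4.2, an unacceptable rating is "defined as any positive response on the digital side effect diary rated unacceptable by the patient". Section 7 adds how the rating arises: "Any positive response to any item will trigger the subject to rate their acceptability of side effects in the following way". Sections 6.2 and 7.3 stop the infusion completely at 12 hours.

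**The concern.** In a 3+3 design, the question for each dosed patient is whether the DLT status is known. Section 11.2 asks instead whether the diary is nearly complete over the full 24 hours. The two tests can disagree. Where they do, a patient who has received the drug and whose outcome is settled is replaced, and a further patient is exposed to fill the place.

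The rule also makes no exception for a patient who has had a DLT and then stops answering diaries. The plan does not say whether her DLT still counts. Under 3.4.1, escalation ends when 2 patients in a cohort of 3 to 6 have a DLT, so the handling of one patient can decide whether the next dose level opens. Two teams following the text could reach different decisions from the same data.

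**Working it through.** **Step 1. How many missed entries reach 20%?** The smallest number is 0.20 × n, rounded up.

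| Source of schedule | Scheduled entries | n | Trigger | Share |
|---|---|---|---|---|
| Appendix 2, side effect diary row | 15, 30 min; 1, 4, 8, 10, 12, 16, 20, 24 h | 10 | 2 | 20.0% |
| Section 7, Side Effect Acceptability Ratings | 15, 30, 60 min; 4, 8, 12, 16, 20, 24 h | 9 | 2 | 22.2% |
| Section 7, Ketamine Infusion procedures | 15, 30, 60 min; 4, 8, 10, 12, 16, 24 h | 9 | 2 | 22.2% |
| Appendix 4, payment lines | 1, 6, 10, 12, 16, 20, 24 h and a second 12 h line | 8 | 2 | 25.0% |

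One missed entry (10.0% to 12.5%) never triggers the rule. The word *responses* is not defined. Counting the seven yes/no symptoms separately, two wholly missed entries are 14 of 70, 14 of 63 or 14 of 56 items, which are the same percentages. The ambiguity matters for partly completed entries and for unscheduled ones.

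**Step 2. Is the DLT status known when the gap is after the infusion?** Take a patient on the Appendix 2 schedule with no DLT by hour 12, complete vital signs to hour 24, and the 16 and 20 hour diaries missed.

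- Hemodynamic part: vital signs have their own row in Appendix 2, including 16, 20 and 24 hours. Known.
- Cessation part: the infusion ended at 12 hours, so it can no longer be stopped because of a rating. Known.
- Section 11.2: 2/10 = 20%. Withdrawn and replaced.

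**Step 3. Is the same true of a gap during the infusion?** No. A positive diary item prompts the rating, and an unacceptable rating starts the hold, reduce and stop sequence of Table 1 in Section 6.3. If the diary is not answered during the infusion, an unacceptable side effect may go unrated and a cessation DLT may be missed.

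**Step 4. How often might the rule be triggered?** The plan has no figure to reproduce, and no miss rate. Assume each entry is missed independently with probability q. Then P(trigger) = 1 − (1−q)^n − n·q·(1−q)^(n−1).

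| q (assumed) | n = 9 | n = 10 |
|---|---|---|
| 5% | 7.1% | 8.6% |
| 10% | 22.5% | 26.4% |
| 15% | 40.1% | 45.6% |

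At q = 10%, the chance that a cohort of three has at least one replacement is 1 − (1 − 0.225)³ = 53% with 9 entries and 1 − (1 − 0.264)³ = 60% with 10. Dosing until 12 patients escape the rule would take about 12/(1 − 0.225) = 15.5 to 12/(1 − 0.264) = 16.3 patients.

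**Step 5. How much of this is the post-infusion part?** In Appendix 2, seven entries fall within the infusion (15 min to 12 h) and three after it. If the 20% threshold applied to the seven alone, it would again take two misses (2/7 = 28.6%), and the same formula with n = 7 gives 4.4%, 15.0% and 28.3% at q = 5%, 10% and 15%. The differences from the n = 10 column are 4.2, 11.4 and 17.3 percentage points. These are patients replaced only because post-infusion entries enter the count.

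**The case against.** The strongest objection is that a completeness rule suits an outcome driven by patient ratings. The diary prompts and records the ratings behind the cessation part of the DLT. RASS is listed among the diary's questions (Section 7, Side Effects) and has its own DLT row in Table 1. Sections 12 and 12.1 word the DLT and the primary outcome in terms of acceptable or unacceptable side effects. On this view the rule implements the Section 1 requirement for complete primary outcome data. The objection stands for the infusion period. A reader might infer that neither part of the DLT definition depends on the diary and that the criterion should be deleted. The documents do not support that: deletion would let a patient with no in-infusion diaries count as free of DLT. The objection does not reach the post-infusion entries, because the non-hemodynamic rows of Table 1 all lead to a DLT through stopping an infusion that has already ended.

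A reader might also infer that replaced patients are discarded from the 3+3 count and that the DLT rate is therefore biased. The plan says they are replaced and restricts only later data; it does not say what happens to a DLT status already observed. Even if removal is assumed, the direction is open. With 10 entries and q = 10%, dropping only non-DLT patients turns a true 20% into 0.2/(0.2 + 0.8 × 0.736) = 25%. Dropping 46% of DLT and 26% of non-DLT patients turns a true 30% into (0.3 × 0.544)/(0.3 × 0.544 + 0.7 × 0.736) = 24%.

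Two smaller points also stand. If unscheduled assessments count as responses, one extra entry on the 10-entry schedule gives 2/11 = 18%, below the limit. And automated alerts, the inpatient setting and $50 per diary line in Appendix 4 favour good completion, so the true miss rate may be low.

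**Conclusion.** The concern holds in this form. Two wholly missed scheduled entries trigger withdrawal and 1:1 replacement, the rule is not tied to DLT evaluability, and a patient who misses two of the post-infusion diaries is replaced although both parts of the Section 3.4.1 definition are settled. A patient with an observed DLT is not exempted.

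This rests on three things: 3.4.1 is the operative DLT definition, as Section 4 indicates; vital signs are complete to 24 hours; and only scheduled entries are counted. The looser wording in Sections 12 and 12.1 could be read to make post-infusion ratings part of the outcome, which is a further reason to state the evaluability rule.

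The frequency is illustrative: about 7-46% of patients for assumed independent miss rates of 5-15% over 9-10 entries. No direction of bias is shown. The change should be made because the rule as written can expose extra patients for no gain in primary information and leaves the counting of an observed DLT unstated.

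**What to change.** In Section 11.2, replace the diary criterion with an evaluability rule for the 3+3 count:

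- (a) Every dosed patient with an observed DLT stays in the count and is not replaced.
- (b) A patient without a DLT is evaluable, and not replaced, if vital signs are complete through the 24 hour window, the infusion record is complete, and diary and acceptability data during the 12 hour infusion meet the completeness threshold. Define *responses* as scheduled entries, and cite one diary schedule, since the four listed above differ.
- (c) Missed post-infusion diaries affect only the secondary acceptability analysis. In Section 12.4, report the number of missed diaries per patient by dose level.

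The cost is wording in 11.2 and 12.4, and no more patients are dosed than now. The small downside is that some counted patients will have incomplete post-infusion acceptability data.

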## 11.3 Clinical Trial Stopping Rules

This study may be suspended, or prematurely terminated if there is sufficient reasonable cause. DSMB will review all events pertaining to participant withdrawals. An independent decision will be made regarding trial discontinuation based on risk assessment for current and future trial participants.

Written notification, documenting the reason for study suspension or termination, will be provided by the suspending, or terminating party to study participants, investigators, funding agency, the IND sponsor, and regulatory authorities. If the study is prematurely terminated or suspended, the PI will promptly inform study participants, the IRB, and sponsor and will provide the reason(s) for the termination or suspension. Study participants will be contacted, as applicable, and be informed of changes to the study visit schedule.

Circumstances that may warrant termination or suspension include, but are not limited to:

- Determination of unexpected, significant, or unacceptable risk to participants
- Demonstration of efficacy that would warrant stopping
- Insufficient compliance to protocol requirements
- Data that are not sufficiently complete and/or evaluable
- Determination that the primary endpoint has been met
- Determination of futility

Study may resume once concerns about safety, protocol compliance, and data quality are addressed, and satisfy the sponsor, IRB and/or FDA.

# 12 Statistical Analysis

By virtue of its design, the maximum tolerated dose (MTD) 3+3 design encompasses a minimum number of 6 and maximum number of 12 patients enrolled in this trial. The results identify the drug dose at which ≥33% of patients experience dose limiting toxicity, which we have defined by unacceptable side effects or adverse events. The number of subjects at each dose is dictated by traditional MTD 3+3 design, balancing the risks associated with the study drug and the assessment of adverse event rates. A formal power calculation was not performed.

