# 12.1 General Approach

The outcome of this design is the determination of the Maximum Tolerable Dose of ketamine infusion post-cesarean delivery. As such, the final dosing of the MTD design is the primary outcome determined as patient report of tolerated dose and acceptable side effect experiences in greater than 66% of patients.

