# 12.3 Analysis of Primary Endpoint

Maximum Tolerated (Ketamine) Dose (MTD): The MTD will be defined as the dose at which fewer than 33% of patients experience intolerable effects.

Tolerability (dichotomous Yes/No)

- Tolerability (YES) will be defined as: lack of serious adverse events (serious adverse event defined as: severe unresolved hemodynamic effect: systolic blood pressure <80 or >160, heart rate <40 or >120).
- *Lack of Tolerability* will be defined as presence of any serious adverse event (i.e., severe unresolved hemodynamic effect: systolic blood pressure <80 or >160, heart rate <40 or >120).

For this MTD study, rates of the primary endpoint will be reported as numbers and percentages. Rates of blood pressure and heart rate events will be reported as numbers and percentages.

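### The printed thresholds for the MTD disagree at 1 of 3 and 2 of 6 DLTs, and Section 12 leaves out the step down from the stopping dose

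*Combined protocol and SAP*

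**What the plan says.** Five statements bear on how the MTD is read from the data.

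- Section 3.4.1, definition: "The MTD will be defined as the dose at which fewer than 33% of patients experience a DLT defined by intolerability".
- Section 3.4.1, stopping rule: "Escalations occur until 2 in a cohort of 3 to 6 experiences DLT". A parenthesis restates this as at least "33% of patients experience DLT at that dose". The next sentence is "The dose below this level estimates the MTD".
- Section 12, opening paragraph: "The results identify the drug dose at which ≥33% of patients experience dose limiting toxicity". No step down follows.
- Section 12.1: the final dose is the primary outcome, judged by patient report of a tolerated dose and "acceptable side effect experiences in greater than 66% of patients".
- Section 12.3: the MTD is "the dose at which fewer than 33% of patients experience intolerable effects".

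Section 4 says that after three patients the options are to escalate, to enter three more at the same level, or to stop. It does not tie an option to a DLT count and refers to Figure 2 for the scheme. Sections 1, 5.1 and 12 give a maximum of 12 patients, and 5.1 gives four dose levels. The visible text sets no order of precedence among these statements.

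**The concern.** In a 3+3 design the decisive outcomes are 1 of 3 and 2 of 6, and both equal one third. A threshold printed as 33% or 66% sits just to one side of that fraction, so the direction of the inequality and the rounding decide the answer. The plan uses a count, a lower-tail percentage, an upper-tail percentage and a tolerated percentage, and treats them as interchangeable.

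The MTD is the trial's only primary result. If the statements part company at these outcomes, two careful readers may differ on whether to stop at a level, or on which level to report, and each can point to a sentence in the plan.

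**Working it through.** **Inputs.** The thresholds are those quoted above. The event is first taken to be the same in every rule; that assumption is examined at the end of step 2. True DLT rates are assumptions. The only related rate in the documents is 1/8 = 12.5% (Section 6.3), which is the share of individuals given a lower infusion rate because of side effects, not a DLT rate.

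**Step 1: the plan's own equivalence.** Section 3.4.1 equates 2 DLTs in 3 to 6 patients with at least 33%. With two DLTs the rates are 2/3 = 66.7%, 2/4 = 50%, 2/5 = 40% and 2/6 = 33.3%, all at least 33%. With one DLT they are 1/3 = 33.3%, 1/4 = 25%, 1/5 = 20% and 1/6 = 16.7%. The equivalence fails at 1/3 only.

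**Step 2: each rule at the outcomes that matter.**

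| DLTs | Rate | Count of 2 or more (3.4.1): stop? | At least 33% (3.4.1): stop? | Fewer than 33% (3.4.1, 12.3): MTD allowed? | Tolerated, more than 66% (12.1): accepted? |
|---|---|---|---|---|---|
| 1/3 | 33.3% | no | yes | no | yes (66.7%) |
| 1/6 | 16.7% | no | no | yes | yes (83.3%) |
| 2/6 | 33.3% | yes | yes | no | yes (66.7%) |
| 2/3 | 66.7% | yes | yes | no | no (33.3%) |

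At 1/3 the two halves of one sentence in 3.4.1 differ on stopping. At 2/6 both halves stop, 12.3 agrees, and only 12.1 accepts the level.

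With exact thirds in place of 33% and 66%, 4/6 is not greater than 2/3, so the 2/6 conflict disappears. The 1/3 conflict stays: 1/3 is at least 1/3, but one is not two.

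The last column equates being free of a DLT with reporting acceptable side effects. Section 3.4.1 requires persistent hemodynamic effects, or complete infusion cessation for intolerable ratings, to make a DLT. Under 3.4.2, a single adverse answer on Burden or Affective Attitude makes the experience unacceptable. A patient without a DLT can therefore fail 12.1. Section 12.3 is narrower again, counting only severe unresolved hemodynamic effects, so its agreement with 3.4.1 at 2/6 requires both events to be of that kind.

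**Step 3: Section 12.** Under 3.4.1 the level with at least 33% DLT is where escalation stops, and the MTD is one level lower. The Section 12 sentence describes the former and does not mention the latter.

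**Step 4: how often a tested level ends at 2/6 by 1/3 then 1/3.** P(1/3) = 3p(1−p)², and P(2/6 by this route) = [3p(1−p)²]².

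| Assumed p | P(1/3) | P(1/3 then 1/3) |
|---|---|---|
| 12.5% | 0.287 | 0.082 |
| 20% | 0.384 | 0.147 |
| 30% | 0.441 | 0.194 |
| 40% | 0.432 | 0.187 |

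These are conditional on the level being opened and on expansion at 1/3.

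**Step 5: outcomes on which the count rule is silent.** A level below the stopping level exists only if some level above the first stops. At an assumed 12.5% at all four levels, with expansion at 1/3 and no cap, a level is passed with probability 0.875³ + 0.287 × 0.875³ = 0.670 + 0.192 = 0.862, and all four with 0.862⁴ ≈ 0.55. The cap adds another case: 0/3, 0/3, 0/3, 1/3 uses 3 + 3 + 3 + 3 = 12 patients and leaves none for expansion.

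**The case against.** The strongest defence is that the plan has an operational rule. Section 3.4.1 gives a count and a step down, Sections 12 and 12.2 invoke the traditional 3+3, and 12.3 matches 3.4.1 at 2/6. On that view 33% and 66% are truncated thirds, the Section 12 sentence only introduces the design, and Figure 2, which is not visible here, may fix the action at 1/3.

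Much of this stands, and it limits what can be claimed. Three stronger readings are tempting and not supported:

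- A reader might infer that the statistical section always reports a dose one level too high. The Section 12 sentence does not use the term MTD and can be read as describing the stopping dose; 12.3 sides with 3.4.1.
- A reader might infer that 1/3 gives two MTDs one level apart from the same data. It is normally an interim result. The rules differ on stopping versus expanding, which leads to different later data. It is final only if the cap is reached there.
- A reader might take the 8% to 19%, or the chance of 1/3 itself, as the chance that a trial gives conflicting MTDs. They are per tested level, at assumed rates, and for 2/6 they also need acceptability to coincide with absence of a DLT.

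The defence does not remove the mismatch inside 3.4.1, which survives exact thirds. Nor does it explain why 12.1 names a differently worded criterion as the primary outcome. Figure 2 could settle the action at 1/3, but the conflicting sentences in 12 and 12.1 would remain.

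**Conclusion.** The point holds as an inconsistency in the printed rules for the primary result.

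- The conflict at 1/3 within 3.4.1 is firm on the text, subject to what Figure 2 shows.
- The conflict at 2/6 between 12.1 and Sections 3.4.1 and 12.3 is conditional. It needs the percentages taken as printed and one common event across the three sections.
- The omission in Section 12 is firm as an omission. It becomes a wrong dose only if that sentence is taken as the trial's result.

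Where the 2/6 conflict applies, the two readings are one dose level apart. The route to 2/6 has probability about 8% to 19% per tested level over assumed DLT rates of 12.5% to 40%. No per-trial figure is offered, because it would need an assumed DLT rate at each of the four levels and a rule for the cap. Correction is warranted before the data are read, since the wording determines which dose the trial declares.

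**What to change.** Reconcile Sections 3.4.1, 12, 12.1 and 12.3, together with Figure 2, to one decision rule expressed as a DLT count on one defined event. Then:

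1. Remove the 33% and 66% statements, or correct them so that they agree with the count at 1/3 and 2/6.
2. State in Section 12 that the MTD is the level below the stopping level, as 3.4.1 says.
3. Use the same event in 3.4.1, 12.1 and 12.3, or report acceptability separately from the MTD decision.
4. State what is declared in three cases: no level stops escalation, the first level stops, or the 12-patient cap is reached with 1/3 at the current level.

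The investigators should choose the rule. The cost is wording in four sections and a check of one figure, with no added patients or procedures.
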